**Expected Result**

1- Baseline binding: We expect increases in baseline binding (i.e. volume of distribution) of PBR28 in the parietal

lobe. This is both where most of the amyloid is deposited in early disease and also the location of the strongest positive findings in the NIMH study.

2- Microglia activation reserve index: We also expect to have significant up-regulation of the microglia activation reserve index. The calculations will be done using the parietal lobe ROI, this is the region that shows the most inflammatory response in our previous study of normal patient with LPS and also where most marked change in the PBR28 binding was found in the NIMH study. However we expect increases in the inflammatory response in the brain diffusely especially affecting the parts which were shown to have increased inflammation at baseline such as precuneus and mesial temporal areas.

### Interpretation

We know of the presence of increased inflammation in AD and not MCI or cognitively normal individuals. This jump in neuroinflammation from MCI to AD may represent increased sensitivity of microglia to stimulus, most specifically constituents of the amyloid plaque. Microglia are activated when they come into contact with molecular patterns which indicate the presence of cell damage or pathogens. If MARI is increased in patients with AD, one may reasonably surmise that the response of the microglia to amyloid may also be stronger compared to subjects with normal cognition or MCI. This transition to a higher microglial reactivity may turn out to be an important step in the progression of AD.

### Pitfalls and Limitations.

1- Small subject numbers: The considerable resources required for applying this paradigm to each patient means that the number of patients that can be enrolled in this study will necessarily be small. However, this grant will serve to collate preliminary data for a larger project which may include larger numbers as well as more longitudinal data, as well as inclusion of patients with mild cognitive impairment.

2- Uptake may represent differing inflammatory phenotype: PBR28 imaging does not differentiate between the different phenotypes of microglial or astrocytic activation (113,114). As such we cannot know with certainty whether the inflammation we are measuring in one patient is directly comparable with another (however to think that LPS will give two different phenotypes of microglial activation seems implausible). For example, it is known that astroglia also express TSPO in the event of inflammation and reactive astrogliosis. However, having done immunohistochemistry on a baboon brain after the administration of LPS we co-localized TSPO like immunoreactivity with morphologically amoeboid (inflammatory) CD68 positive cells and not with GFAP positive astroglia or resting microglia (106).

3- Activation by LPS is not supramaximal: For a quantitative assay a supramaximal stimulation of the immune system with LPS may seem desirable. However, using 100,000x more potent doses of LPS in baboons than in humans (109), we had similar immune responses of 30-60%.

4- Selection bias due to LPS side effects: The application of LPS to elderly patient will prompt us to exclude more frail elderly from our experiment for fear of complications. This would introduce a selection bias which will be partially addressed with having similar selection processes for the normal controls also.

### Secondary Analyses:

- a- Effects of aging on MARI: Senescent microglia increase their propensity to up-regulate in response to the presence of DAMPs and PAMPs and takes longer to deactivate after these influences are removed (66). In the elderly there appears to be an up-regulation of pro-inflammatory cytokines and MHC Class II expression increasing the propensity of microglia to be activated (112). We aim to demonstrate the efficacy of LPS stimulated PBR28 imaging in showing age related changes in immunity.
- b- Effects of amyloid on MARI: Additionally, we will have the opportunity to explore whether exposure to amyloid increases the reactivity of the microglia to stimulation. This may be achieved by correlating the microglia activation reserve index with the amyloid regional SUVRs. If there is a correlation and we suspect that there will be then this may suggest a mechanism for the dysregulation of the innate immunity in AD.
- c- Effects of MARI on cognition: we will compare the result of the neuropsychological testing with MARI and baseline inflammation. If inflammation is one of the determinants of neuronal damage, then one may expect to find worse cognition in areas with higher inflammation. This will likely reflect the observe inflammation pre-LPS rather than the capacity of the microglia to react. We will also make two composite scores: an executive and a memory composite. These will be formed by averaging the Z scores of the individual test pertaining to executive or memory function. We will then correlate these with frontal and mesial temporal inflammation.

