- a) Effects of aging on MARI: We will evaluate the effects of aging on MARI. Comparisons will be made for MARI between cognitively normal elderly and the 8 healthy individual to whom we applied this protocol in an earlier study. The reactivity of microglia is reported to increase with age (11) and so we expect MARI to increase in the cognitively normal elderly. However, we expect the differences between the young and elderly cognitively normal subjects to be small relative to the comparison of AD and elderly normal controls.
- b) Effects of amyloid on MARI: We will look at the relationship of regional and global amyloid load to MARI. The presence of a relationship suggests that one of the reasons for increased microglial reactivity might be interactions of microglia with pathologic amyloid.
- c) Effects of MARI on cognition: We will explore whether MARI would correlate with measure of disease stage, with higher MARIs associated with worse neuropsychological score and more severe disease. We will look for correlations between MARI and the individual neuropsychological scores. This would determine if disease severity is correlated with microglial activation reserve.

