**PET Imaging of TSPO in AD**

We will compare PBR28 binding site availability in brain regions of 7 living human subjects who have AD with that in 7 age-matched healthy controls by using the ligand  $^{11}\text{C}$ -PBR28 and PET. Dose of LPS (see below) will be administered intravenously and the subject will be reimaged at 180 minutes after the injection. Considering possible failures in scans, a total of 16 patients will be studied in 2 groups, cognitive normal AND amyloid negative versus clinical criteria for mild AD and amyloid positive to reach our goal of 7 successfully scanned subject for each group. The detailed protocol may be found

09/29/12 Version 13

in our previous publication (109). We expect that 20-30% of cognitively normal participants who receive amyloid scans under this protocol will be amyloid positive. Therefore, we will enroll up to 10 participants in the cognitively normal cohort to attain the goal of 7 participants who are cognitively normal AND amyloid negative.

Primary Outcome:

The 16 enrolled subjects will have C-PBR28 using the bolus/infusion method. Measurements will be made at baseline and 180 minutes after the injection of LPS. We will measure Total Volume of Distribution (VT) for 12 brain regions defined by MRI scan, as described (111). All primary outcomes will use the parietal ROI for calculations of both baseline activation and microglial activation reserve. For our primary outcomes we will choose the microglia activation reserve index defined as MARI =  $[(VT(LPS)-VT(\text{baseline}))/ VT(\text{baseline})] \times 100$ . In the NIMH study the greatest difference in the regional PBR28 binding between AD and cognitively normal subjects was found in the parietal lobe (7). We also found the greatest microglia activation reserve index in the parietal lobe when we applied our paradigm to young healthy controls (109). Other ROIs will be used in secondary analyses.

Statistical Considerations and Sample Size:

Several comparisons of C-PBR28 VT brain level and microglia activation reserve index in the parietal lobe will be made using Student T-test to test for a difference between group means: young healthy group vs. elderly cognitively normal, as well as AD vs. elderly cognitively normal.

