**Inclusion Criteria:**

a- Mild AD Subjects:

1. NIA-Alzheimer's Association core clinical criteria for probable AD
2. Age between 55 and 90 (inclusive)
3. Score on the MOCA greater than or equal to 17
4. Presence of a responsible caregiver who will accompany AD subjects to all procedures.
5. Biomarker evidence of Alzheimer's disease via an amyloid PET scan or CSF amyloid  $\beta$  measurement.
6. The patient should have a capacity to consent.
7. CDR global score greater than 0.

b- Cognitively normal elderly Subjects:

1. Absence of NIA-Alzheimer's Association core clinical criteria for probable AD
2. Objective memory scores within normal range for age (do not meet MCI Subjects criterion 2)
3. Age between 55 and 90 (inclusive)
4. CDR global score of 0.0

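### The exploratory correlations of MARI with amyloid and cognition have no group term or within-group estimate, so a pooled correlation cannot support the amyloid or severity reading attached to it

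*Combined protocol and SAP*

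**What the plan says.** Section V.1 (Statement of Purpose) lists exploratory analyses a to c, and the Secondary Analyses section repeats them.

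- **Amyloid (b).** The method is given in Secondary Analyses: "This may be achieved by correlating the microglia activation reserve index with the amyloid regional SUVRs". The reading follows: "If there is a correlation and we suspect that there will be then this may suggest a mechanism for the dysregulation of the innate immunity". Section V.1 b puts it this way: "The presence of a relationship suggests that one of the reasons for increased microglial reactivity might be interactions of microglia with pathologic amyloid".
- **Cognition (c).** Section V.1 c says: "We will look for correlations between MARI and the individual neuropsychological scores". It expects higher MARI with worse scores and adds: "This would determine if disease severity is correlated with microglial activation reserve". Secondary Analyses c is more cautious. It expects the cognition link to reflect inflammation before LPS more than the capacity of microglia to react.
- **Groups.** PET Imaging of TSPO in AD defines them as "cognitive normal AND amyloid negative versus clinical criteria for mild AD and amyloid positive", with a target of 7 successful scans in each. The Inclusion Criteria separate them on cognition as well: CDR above 0 for AD, CDR 0 with normal memory scores for CN.
- **Amyloid measurement.** AD criterion 5 accepts "Biomarker evidence of Alzheimer's disease via an amyloid PET scan or CSF amyloid". The PET for amyloid section foresees PiB only where needed, up to 10 scans. The MRI section says that a screening PiB scan will be obtained.

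No section says whether the correlations pool the groups, and none gives a diagnosis term or a within-group estimate. Pitfalls and Limitations lists four items; this is not one of them.

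**The concern.** The two variables to be correlated with MARI are also the ones that define the groups. In a pooled AD-plus-CN sample, amyloid load and cognitive score partly stand in for diagnosis. If MARI differs by diagnosis, which is the primary hypothesis, it will tend to correlate with both even when neither is related to MARI inside either group.

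The Background argues that amyloid load alone does not explain the step in binding from MCI to AD, so separating amyloid from disease state is central to the study's question. A pooled correlation does not separate them. The protocol also describes the study as preliminary data for a larger project, so a correlation read as pointing to amyloid or to severity could shape that project while adding little to the primary contrast.

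**Working it through.** **The plan's own figure.** The documents give no figure for the correlations. Their power statement for baseline binding is a detectable effect above 1.6 at alpha 0.05 and power 0.80. A two-sided t-test with 7 per group gives a detectable effect of 1.63, and power of 78.5% at 1.6, so that figure reproduces. For MARI the plan states more than 2. With 7 per group, power at 2 is 92.9%; that mismatch is a separate matter. I use 1.6 and 2 only as the plan's own scale for a MARI difference.

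**Inputs**
- n = 7 AD and 7 CN (Section V.1).
- dM, the AD–CN difference in MARI in within-group SDs: 1.6 and 2.
- dA, the AD–CN gap in SUVR or in a cognitive score, in within-group SDs: not given in the documents; assumed 2 to 4.
- Within-group correlation: 0.

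**Pooled correlation, equal groups**

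r = 0.25·dM·dA / √[(1 + 0.25·dM²)(1 + 0.25·dA²)]

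For dM = 2 and dA = 3: 1.5 / √(2 × 3.25) = 1.5 / 2.55 = 0.59.

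The rejection rates come from 40,000 simulated trials per scenario (two-sided 5% Pearson test).

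| dM | dA | pooled r (formula) | pooled test significant |
|---|---|---|---|
| 1.6 | 2 | 0.44 | 41% |
| 1.6 | 3 | 0.52 | 57% |
| 1.6 | 4 | 0.56 | 66% |
| 2 | 2 | 0.50 | 52% |
| 2 | 3 | 0.59 | 73% |
| 2 | 4 | 0.63 | 82% |

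With dM = 0 the rejection rate is 5%, so the excess comes entirely from the group difference. With diagnosis partialled out, the mean r is 0.00 and rejection is about 5% in every scenario. As dA grows, r tends to the correlation between MARI and group membership: 0.62 at dM = 1.6 and 0.71 at dM = 2.

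**Adding amyloid-positive CN participants.** CN participants are scanned whatever their amyloid status (PET for amyloid). Up to 10 are to be enrolled, with 20–30% expected positive, so 2 to 3 people. Take three, with CN-level MARI and AD-level amyloid (7+7+3 = 17):

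- covariance = dM·dA × (7/17)(7/17) = 0.170·dM·dA
- variances = 1 + (70/289)·dM² and 1 + (70/289)·dA²
- at dM = 2 and dA = 2, 3, 4: r = 0.678/1.969 = 0.34; 1.017/2.502 = 0.41; 1.356/3.098 = 0.44

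The simulated means are 0.36, 0.42 and 0.45, with rejection rates of 28%, 39% and 45%. This dilution applies to the amyloid correlation only. The same three people have CN-level cognition, so they do not weaken the cognition correlation in this way.

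**Precision of the alternatives.** By Fisher's z, the true r needed for 80% power is tanh[(1.960 + 0.842)/√(n − 3 − k)], where k is the number of variables adjusted for. Adjusted for diagnosis at n = 14: tanh(2.80/√10) = 0.71. Within one group of 7: tanh(2.80/√4) = 0.89.

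**The case against.** The strongest reply has four parts.

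1. *Pooling is inferred.* This is true. The severity wording in Section V.1 c could describe an analysis within patients, and the regional SUVR wording could describe one across regions. The text specifies neither, and its plain reading is one correlation over everyone scanned.
2. *The analyses are exploratory and the amyloid reading is hedged.* This also stands. Hedging limits the claim, but it does not let a pooled correlation separate amyloid from diagnosis. The severity sentence in Section V.1 c is not hedged.
3. *Amyloid-positive CN participants break the link between amyloid and diagnosis.* They weaken it materially, but rejection of 28–45% is still far above the nominal 5%.
4. *Adjustment is not a full cure.* This is correct. At gaps of 2, 3 and 4 SD the variance inflation from including diagnosis is 1 + dA²/4 = 2, 3.25 and 5. If amyloid is itself the route to the AD difference, adjustment removes part of the effect sought.

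A reader might go further and infer that a positive primary result would almost automatically deliver an amyloid mechanism and a severity relation as separate support. The documents do not support that. The rates above run from 28% to 82%, no section counts the correlations as independent confirmation, and Secondary Analyses c does not attribute the cognition link mainly to MARI. Nor can one say that SUVR will be missing for some participants: the MRI section promises a PiB scan, while other sections allow entry without one.

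**Conclusion.** The point holds as a limitation of exploratory analyses b and c. If the groups are pooled, neither the amyloid reading nor the severity reading follows from a correlation, because a MARI group difference alone would often produce one. At a MARI difference of 2 SD the size is r of about 0.50 to 0.63 with significance in 52–82% of trials at 7+7. For amyloid with three amyloid-positive CN participants added, it is about 0.36 to 0.45 and 28–45%.

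These figures rest on zero within-group association, on an assumed gap of 2 to 4 SD that the documents do not supply, and on a MARI difference that the plan calls detectable and does not claim to expect. Any real within-group association would be mixed into the pooled value; the point is that the pooled value alone cannot show it. The primary AD versus CN comparison does not depend on any of this.

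**What to change.** In Section V.1 (exploratory analyses b and c) and Secondary Analyses b and c:

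- State the analysis set. Beside any pooled correlation, report within-AD and within-CN estimates and a diagnosis-adjusted partial correlation, each with a 95% CI, and plots with the groups marked.
- State that the pooled value cannot separate amyloid or severity from diagnosis.
- Include any scanned amyloid-positive CN participants in the within-CN estimate, and say whether they enter the pooled one.
- Reconcile the PET for amyloid section, the MRI section and AD inclusion criterion 5 on whether every participant will have a PiB SUVR, and report the number who do.

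This needs no extra participants or scans. The cost is weak inference: 80% power needs a true r of about 0.71 (adjusted, n = 14) or 0.89 (one group of 7), so the intervals will be wide. Because adjustment may also remove some real amyloid effect, the adjusted estimate should accompany the pooled one and not be the only model.

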the microglia with constituents of the amyloid plaques. The NIMH study (7) of PBR28 binding in patients with AD, MCI and normal cognition showed increased binding in the AD group compared to the other two groups. Equally as important was the finding that there was no significant difference in the PBR28 binding of MCI patients compared to normal controls. Most of amyloid deposition occurs before the onset of symptoms and the rate of amyloid increase plateaus in MCI, so that patients in early AD on average have a relatively small increment in their amyloid deposition compared to MCI (8). The difference in immune activation in AD and MCI may represent differing microglial sensitivity to molecular patterns that activate them for example amyloid plaques. To test this hypothesis, we need to know both the state of activation of microglia and the microglia capacity to activate (activation reserve) which we have defined as reactivity of microglia to a given stimulus. Activation status of microglia depends on a variety of factors including the presence of peripheral inflammation, age and the amount of amyloid present in the brain, whereas microglial activation reserve is more likely influenced by genetics, senescence and regulation of microglia.

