### Procedure

#### Screening and selection procedures:

*Screen/Baseline visit to ADRU:* Each subject will have an initial screening visit that will include:

Screening: Demographics, history, examination, GDS, EKG, Labs, MOCA, logical memory I/II, CDR and Informed consent. Baseline: WAISIII – picture completion, digit symbol, symbol search, arithmetic, digit span, information, letter number sequencing, RAVLT, Trails A/B, Boston naming, Stroop, FAS, Rey complex figure, ADCS-ADL, CAM and NPI. In certain cases, this can take more than 4 hours and we may need to split the day into two where screening and baseline are administered on separate days.

*Possible pre-imaging visit to MRRC:* Many of the patients who will enroll will already have clinical MRI. For those who do not we will organize one for this research.

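### The correlations of cognition with brain inflammation carry no age or group term, so age, and the pooling of AD with control subjects, can produce a correlation on their own

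*Combined protocol and SAP*

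**What the plan says.** Section V, Secondary Analyses, item c (Effects of MARI on cognition), describes two composites. The construction rule is one sentence: "These will be formed by averaging the Z scores of the individual test pertaining to executive or memory function". The analysis is another: "We will then correlate these with frontal and mesial temporal inflammation". The tests in each composite are not listed, the reference for the Z scores is not named, and no covariate is given. The exploratory list in Section V.1 (Statement of Purpose), item c, adds correlations of MARI with disease stage and with the individual test scores, and expects a direction: "with higher MARIs associated with worse neuropsychological score and more severe disease". No covariate is named there either.

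On age, the Background (V.2) says: "Activation status of microglia depends on a variety of factors including the presence of peripheral inflammation, age and the amount of amyloid". It also describes microglia as becoming more reactive with normal ageing. Section V.1, exploratory item a, expects MARI to rise with age. The Inclusion Criteria (V.7) admit ages 55 to 90 in both groups and judge the memory of control subjects against age: "Objective memory scores within normal range for age". That age reference is not carried over to the composites.

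**The concern.** By the protocol's own account, age acts on the imaging side of these correlations, whether inflammation means baseline binding or MARI. Age commonly acts on raw cognitive scores too, and judging control subjects' memory relative to age implies as much. A variable that raises one side and lowers the other produces a negative correlation, which is the direction the plan predicts.

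Matching the groups on age does not prevent this. It balances the comparison of AD with controls but leaves the age spread inside each group, and a correlation across subjects uses that spread.

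Diagnosis works in a similar way. AD subjects are expected to have more inflammation and have lower scores by selection. Pooling the groups can therefore give a correlation even when the two measures are unrelated within each group. The study is meant to supply preliminary data for a larger project, so a correlation that only reflects age or diagnosis could be carried forward as a lead.

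**Working it through.** **The plan's own figure.** The documents give no power or size for the composite correlations. The nearest figure is the detectable effect above 1.6 for baseline activation. With 7 per group, a two-sided t-test at 0.05 and 80% power, the detectable standardised difference is 1.63, so that figure reproduces. It is used below only as an illustrative group gap in inflammation.

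**Inputs.** From the documents: 7 AD + 7 controls = 14 analysable subjects, and alpha 0.05. Assumed: two-sided tests, the age correlations, the group gap in cognition, and the correlation among tests.

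**1. Age alone.** If age correlates a with inflammation and −b with the score, and nothing else links them, the induced correlation is r = −a × b. Rejection rates at n=14 were simulated with 200,000 runs per row:

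| a = b | induced r | false positives, unadjusted | age partialled out |
|---|---|---|---|
| 0.2 | −0.04 | 5% | 5% |
| 0.3 | −0.09 | 6% | 5% |
| 0.4 | −0.16 | 8% | 5% |
| 0.5 | −0.25 | 14% | 5% |
| 0.6 | −0.36 | 25% | 5% |

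**2. Group alone.** Take no relation within either group, a standardised gap of dI in inflammation and of dC in cognition, and equal groups. The pooled correlation is

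r = −(dI/2)(dC/2) / √[(1 + dI²/4)(1 + dC²/4)].

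- dI = 1.6, dC = 1.0: −(0.8 × 0.5)/√(1.64 × 1.25) = −0.28; 17% rejection at n=14.
- dI = 1.6, dC = 2.0: −(0.8 × 1.0)/√(1.64 × 2.00) = −0.44; 40% rejection.
- With a smaller gap, dI = 0.8, dC = 1.0: −0.17; 9% rejection.

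In the same simulations a group term brings each of these back to 5%. An age term alone does not: with age unrelated to either measure, rejection for the two dI = 1.6 cases is still 16% and 37%. Conversely, where age varies within each group, a group term alone leaves that path open.

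**3. Cost of adjustment.** The critical value is |r| = t/√(df + t²), where t is the two-sided 5% point and df = n − 2 − number of covariates. At n=14:

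- no covariate: 2.179/√(12 + 2.179²) = 0.532
- age: 2.201/√(11 + 2.201²) = 0.553
- age and group: 2.228/√(10 + 2.228²) = 0.576

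**4. Score direction (minor).** The battery includes "RAVLT, Trails A/B, Boston naming, Stroop, FAS, Rey complex figure". Some of these may be scored as time, where a higher value is worse. Suppose m of k equally weighted tests with common correlation ρ are left unreversed, and let S = k − 2m. The composite's correlation with any outcome is then proportional to S/√[k(1 − ρ) + ρS²]. Relative to full alignment, for ρ from 0.3 to 0.7, one unreversed test of three keeps 0.47 to 0.71 of the correlation, one of four keeps 0.69 to 0.88, and one of six keeps 0.86 to 0.96. The correlation becomes zero only when exactly half are unreversed, and changes sign only when more than half are.

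**The case against.** The best defence is that the plan is brief rather than wrong. It does not say the Z scores are raw. If they come from age norms, the path from age to cognition is largely closed, and the team does use an age reference for control eligibility. The range 55 to 90 is an eligibility limit and not the observed spread of seven people per group. The age correlations are assumed, and at 0.2 to 0.3 on each side the inflation is negligible (5% to 6%). For MARI, the protocol expects even the difference between young and elderly subjects to be small relative to that between AD and controls. The analysis is exploratory, in a stated pilot that admits its small numbers.

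All of that stands, and it limits the size of the point. It does not remove it: age norms are not stated, the protocol names age as a driver of both activation and reactivity, and the group path does not depend on age at all.

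A reader might also infer three stronger things that the documents do not support.

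- *That timed tests cancel the others in the composites.* No section says how any test is scored, and nothing bars reversing scores before averaging, which a competent analyst would do. None of the listed memory tests is described as timed, so this could concern only the executive composite. With a minority of tests unreversed, the correlation is weakened but keeps its sign.
- *That the cognition question rests on the composites alone.* Section V.1 also plans correlations with individual scores, where a wrong direction would be easy to see.
- *That a correlation would be reported as proof that inflammation damages neurons.* Secondary Analyses, item c, states that link as a premise for what one may expect, and not as a planned conclusion.

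**Conclusion.** The point holds as a gap in adjustment. The correlation as planned has no age or group term, and nothing else stated in the plan closes either path. If the Z scores are not age-normed, and if age correlates 0.2 to 0.6 in size with each side, the false-positive rate at n=14 is 5% to 25% instead of 5%. Pooling the groups gives 9% to 40% under the assumed group gaps shown, with or without age norms. These are illustrations from assumed inputs and not estimates for this sample. The primary comparison of MARI is not affected. Because the analysis is exploratory, this is an inexpensive improvement worth making and no threat to the study. Score direction is a matter of missing detail only.

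**What to change.** Amend Secondary Analyses, item c, and apply the same rule to the correlations of MARI with cognition in Section V.1, exploratory item c:

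- Make each correlation a partial correlation adjusted for age, or use age-normed Z scores for every test in the composite.
- Also adjust for diagnostic group, or report the correlation within group.
- Label the results exploratory.
- State in the same sentence that tests scored as time or errors are reversed before averaging, so that higher means better. This matters for the executive composite only.

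The cost is a few lines of text and no new data. Age takes one degree of freedom (critical |r| at n=14 from 0.532 to 0.553) and group takes one more (0.576 with both). Reporting within group instead leaves n=7, where the critical |r| is 0.754, so those values serve as description. Adjusting for group also sets aside the part of the relation that lies between AD and controls, but the plan already compares the groups directly.
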